## 6.3 Sample Image Number and Blinding

### 6.3.1 Participant Number Assignment

Participant No. will be assigned to participants satisfy the eligibility criteria and are included in the study.

The following rules will apply to generating Participant No:

Participant No.
R - ___ - ___
2 letter site acronym, 3-digit sequence (e.g., R-KO-001, R-KO-002)

The following rules will apply to generating Specimen No.:

Specimen No.
Participant No. - ___ - ___
1 letter specimen classification, 1-digit sequence (e.g., R-KO-001-C-1, R-KO-001-P-1, R-KO-001-N-1)

Each selected image will be assigned an enrollment number in a sequential manner. The investigator will register the images by entering such information as the participant number, image type, and order.

### 6.3.2 Reference Standard and Analysis Number Assignment

Reference standard and analysis No. will be assigned according to type as follows:

<Reference standard No.>

- Permanent section analysis (PS): Participant number – Specimen number – permanent section (e.g., R-KO-001-C-PS-01)

<Frozen section No.>

- Frozen section analysis (FS): Participant number – Specimen number – Frozen section (e.g., R-KO-001-C-FS-01)

<cCeLL image analysis No.>

- Pathologist 1 analysis of cCeLL image: Participant number – Specimen number – cCeLL – pathologist (e.g., R-KO-001-C-01-CC-H)

#### **6.4 Informed Consent**

Informed consent must be obtained prior to conducting any study-related assessments. A clinical staff member within the patient's circle of care (known to the patient), who is not part of the research team, will make first contact with potential patients to assess whether or not they are interested in learning more about the study. Then, they will contact a research study team member (not part of the patient circle of care) to discuss the study with the patient and obtain informed consent to participate in the study.

The research staff (not part of the patient's circle of care) will explain the clinical study to each potential participant, including all aspects of the clinical study that are relevant to the participant's decision to participate throughout the clinical study including, but not limited to, the following: purpose and nature of the study, study procedures, expected study duration, available alternative therapies, and the benefits and risks involved with study participation and the potential treatment. They shall avoid any coercion or undue improper influence on, or inducement of, the participant to participate and will not waive or appear to waive the participant's legal rights. Participants will be given a copy of the informed consent form and will be provided ample time to read and understand the document and the opportunity to ask questions. Participants will be informed of their right to withdraw from the study at any time without prejudice; consent forms will use local non-technical language and be provided in a language understandable to the participant. After this explanation, and before any study-specific procedures have been performed, the participant and the PI's qualified designee (a member of the study team outside the patient's circle of care), responsible for conducting the informed consent process will voluntarily sign and personally date the informed consent form. Prior to participation in the study, the participant will receive a copy of the signed and dated written informed consent and any other written information provided to the participant.

#### **6.5 Demographics and Anthropometric Profile**

Demographic information relating to the participant's age and sex will be recorded after enrollment.

#### **6.6 Timing Data**

Start and stop times and other similar data will be collected to determine the processing duration for each test from start to finish.

#### **6.7 Assessment Data**

Test results will be collected and compared from all three (3) modalities (cCell, FS, PS). Blinded assessments of cCell images will be documented from the site pathologist for each analyzable image.

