Permanent section	PS	PS															
Frozen Section	FS	PS															

Study Endpoints	

- The probability of interpretation results by the interpreting physician (1 pathologist) being positive given that the reference standards is positive

- The probability of interpretation results by the interpreting physician (1 pathologist) being negative given that the reference standards is negative

 
Primary Endpoint
 
The primary endpoints in this study are the agreement between cCeLL Ex vivo and frozen section, the sensitivity of cCeLL ex vivo and frozen section, and the specificity of cCeLL ex vivo and frozen section. These endpoints will be assessed by a single pathologist in the analysis of tumor tissue.
 
Secondary Endpoints
 

1. Comparison of time taken in tissue scanning, visualization, and interpretation using cCeLL – Ex vivo to time taken in frozen section analysis.

2. Accuracy in determining the tumor type

3. Required image counts for adequate analysis and diagnosis using cCeLL – Ex vivo

4. Non-diagnostic Image

5. AUC value

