## 6.2 Study Assessments and Procedures

There will be up to three (3) tissue sample types assessed for each participant: 1- center-of-tumor, 2- normal tissue (collected from inevitable standard resection), and 3- margin tissue. Depending on each participant's circumstance, the number of sample tissues harvested will differ from minimum of one to maximum of three. All tissue samples will be assessed with the investigative device and compared against frozen section analysis.

1. Samples will be collected from consented participants who have satisfied the eligibility criteria.
2. Tissues will be removed as part of the standard neurosurgical procedure. Normal tissues obtained from inevitable resection during the course of surgery.
3. Collected samples will be processed as follows:
  1. Wash the biopsied tissue with Phosphate Buffered Saline (PBS)
  2. Place the tissue on a glass slide
  3. Apply dye onto the tissue
  4. After 1 minute, wipe on gauze and then scan (i.e., cCeLL imaging) the tissue using Pixecton (probe) connected to cCeLL – Ex vivo
  5. Send the processed tissue to pathology to obtain images in the form for frozen sections analysis (FS)/permanent sections analysis (PS)
4. Image recordings of sample tissue using cCeLL – Ex vivo are taken and the obtained data is stored (CC).
5. cCeLL – Ex vivo image data of the collected samples is sent to the central core.
6. The result of frozen section analysis (FS) will be collected from the pathology department of each site.
7. The result of permanent section analysis (PS) of corresponding paraffin-embedded tissue section (PS) will be collected from the pathology department of each site. PS will serve as a reference standard to the analysis result of CC and FS.
8. An interpreting pathologist will analyze given images (CC) and is not allowed to review the reference standards (PS).
9. The cCeLL – Ex vivo image data will be de-identified such that only the unique reference numbers will be displayed in the images provided, and participant information including participant enrollment number and surgery information will be removed.
10. The types of the images obtained from this procedure are as follows:

cCeLL – Ex vivo will capture image data of a resected tissue, prior to frozen sectioning (FS) and permanent sectioning (PS). The sample is used to evaluate the presence or absence of tumors, and also to evaluate the tumor types.

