## **8. Study Evaluation**

### **8.1 Primary Endpoint**

The primary endpoints in this study are the agreement between cCeLL Ex vivo and frozen section, the sensitivity of cCeLL ex vivo and frozen section, and the specificity of cCeLL ex vivo and frozen section. These endpoints will be assessed by a single pathologist in the analysis of tumor tissue.

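### Section 6.7 takes the cCeLL reads from the site pathologist, while the rest of the plan describes one interpreting pathologist, and no passage keeps that reader independent of the frozen-section result

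*Combined protocol and SAP*

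**What the plan says.** All references are to the combined protocol and SAP.

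- Section 6.7: "Blinded assessments of cCell images will be documented from the site pathologist for each analyzable image".
- Section 8.1, on the three primary endpoints (agreement, sensitivity, specificity): "These endpoints will be assessed by a single pathologist in the analysis of tumor tissue".
- Synopsis, definition of sensitivity: "The probability of interpretation results by the interpreting physician (1 pathologist) being positive given that the reference standards is positive". The synopsis again names one pathologist for the tumor-type endpoint.
- Section 6.2, item 5: "cCeLL – Ex vivo image data of the collected samples is sent to the central core". Neither section 6.2 nor the synopsis says what the core does with the images.
- Section 6.2, item 8: "An interpreting pathologist will analyze given images (CC) and is not allowed to review the reference standards (PS". The synopsis has the same bar, lasting until all interpretations are complete. Neither version mentions FS.
- Section 6.3.2 provides one code for the read: "Pathologist 1 analysis of cCeLL image: Participant number – Specimen number – cCeLL – pathologist".
- Section 6.2, item 6: "The result of frozen section analysis (FS) will be collected from the pathology department of each site". Item 7 takes PS from the same source: "paraffin-embedded tissue section (PS) will be collected from the pathology department of each site".
- The synopsis lists four sites. Section 5.4.1 allots them 36, 57, 57 and 100 analyzable samples.

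**The concern.** The cCeLL read enters all three primary endpoints, and the plan does not settle who makes it. One pathologist for the study and a site pathologist at each of four sites are different designs. With one reader, the result describes one person's performance. With site readers, it averages up to four people, and section 8.3.1 has no reader or site term. Sites that follow different sections would contribute different kinds of read to one pooled test.

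The second issue is independence. FS is one side of the agreement endpoint and the comparator for sensitivity and specificity. A reader who knows the FS call, or made it, may repeat it on the cCeLL image. Agreement then rises without any change in the device. The same mechanism pulls the FS-minus-cCeLL differences towards zero and reduces the discordant pairs that set the standard error in 8.3.1. Both effects favor a finding of non-inferiority.

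**Working it through.** **Setting the text side by side.** The plan states no figure on this point, so there is none to reproduce.

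1. *Number of readers.* 8.1, the synopsis and the single CC-H code in 6.3.2 point to one. 6.7 at four sites points to as many as four.
2. *Place of reading.* 6.2 sends the images to a central core and then has an interpreting pathologist read them. No sentence places that pathologist at the core. 6.7 places the reader at the site.
3. *Independence.* PS is barred. FS is not. No passage says that the cCeLL reader must not have issued the FS report on the same sample.

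**What site readers would contribute (section 5.4.1).** The totals check: 36 + 57 + 57 + 100 = 250; cancer 30 + 50 + 50 + 70 = 200; normal 6 + 7 + 7 + 30 = 50. With one reader per site, the four readers would supply 14.4%, 22.8%, 22.8% and 40% of all reads. One reader would supply 30/50 = 60% of the normal samples and 70/200 = 35% of the cancer samples.

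**Illustration of carry-over from FS.**

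Inputs from section 8.3.1: n = 250, null agreement 80%, exact binomial test, anticipated sensitivity and specificity about 90% for each method.

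Assumptions that are not in the plan: a one-sided 2.5% level (no level is stated for the agreement test), independent errors as the starting point, and a share c of samples in which the reader simply repeats the FS call.

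- Agreement with independent errors: 0.9 × 0.9 + 0.1 × 0.1 = 0.82.
- Agreement with carry-over: c + (1 − c) × 0.82 = 0.82 + 0.18c. This gives 0.838 at c = 10% and 0.865 at c = 25%.
- Critical count at one-sided 2.5%: 213 of 250, with P(X ≥ 213 | 0.80) = 0.021. At one-sided 5% it is 211, with probability 0.045.

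| Carry-over c | True agreement | Pass, one-sided 2.5% | Pass, one-sided 5% |
|---|---|---|---|
| 0 | 82.0% | 11% | 18% |
| 10% | 83.8% | 31% | 44% |
| 25% | 86.5% | 76% | 86% |

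For comparison, at the 86% agreement used in 8.3.1 the pass probabilities are 68% and 80%.

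**The case against.** **The text can be reconciled.** A single pathologist could mean one reader per image, which removes the literal contradiction. This stands as a possible reading, but it produces the pool of local readers, still without a rule on FS.

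**The reads are blinded.** 6.7 says so, and 6.2 removes participant and surgery information from the images. Moreover, someone who issued the PS report on a sample has reviewed it, and so cannot comply with the PS bar and also read that sample. This stands. A reader might infer that one person could call the index test, the comparator and the reference standard on the same tissue; the PS bar already limits that. It does not cover FS. The FS gap would exist with a central reader too, although 6.7 makes overlap easier.

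**Shared identity is inferred.** The plan says only that FS and PS come from each site's pathology department. It does not say that the cCeLL reader works there or signs those reports. Nor does it give a reading schedule that would show that a pathologist must recognise a case. This stands: the plan permits overlap but does not prescribe it.

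**The numbers are illustrative.** No carry-over rate has a source, and 82% is a product of the independence assumption. The plan cites pilot agreement above 86%, so the 11% pass rate is not its own scenario. This also stands.

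**Site mix is not caused by 6.7.** One site supplies 60% of the normal samples under any reader arrangement, and each comparison is paired within sample. That too is correct. What 6.7 adds is that reader and site become confounded.

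**Conclusion.** The conflict is real and lies between current sections. Up to 250 of 250 primary reads depend on how it is resolved. Following 6.7 as written would pool up to four local readers from the institutions that supply FS and PS, with no bar on knowing the FS result or having issued it. The likely direction of bias is towards agreement with FS; its size is unknown. The pass probabilities of 11%, 31% and 76% rest on an assumed level, independent errors and assumed carry-over of 0, 10% and 25%. They show that modest carry-over could matter, not that it will occur.

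Two stronger conclusions are not supported. The plan does not establish that the intended reader sits at the central core; it only sends image data there. It also does not show that several readers are in themselves a flaw. Site readers could be acceptable if they were declared, kept independent sample by sample, and accounted for in the analysis.

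**What to change.** 1. In 6.7, replace the site pathologist by the single interpreting pathologist of 6.2, 6.3.2, 8.1 and the synopsis, and define the role of the central core.
2. In 6.2 item 8 and the matching synopsis step, state that this reader is blind to FS as well as PS, and has issued neither report on any sample that he or she reads.
3. In 8.1, state that the single pathologist refers to the cCeLL read, and that FS and PS are the site departments' reports.
4. If site readers are in fact intended, say so throughout, apply the same independence rule to each sample, and report and account for reader or site in the primary analysis.

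The cost is mainly wording. Any images already read by a local reader who was not independent would need re-reading for the primary accuracy analysis. The synopsis measures cCeLL reading time from image capture to the final reading, so the original reading times should be kept for secondary endpoint 1; a later re-read would distort that interval.

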## 7. Risks and Procedures to Minimize Risk

### 7.1 Anticipated Risks

The investigational medical device used in this prospective study is an ex-vivo diagnostic device which has no direct or indirect effect on the participant, and therefore there are no anticipated risks to be identified. Standard of care diagnostic images will be used to make clinical decisions in this study population.

### 7.2 Precautions of Use

#### 7.2.1 General Precautions

1. To be used for ex-vivo diagnostic purposes only (for trained professionals only).
2. To be used by a trained professional only.
3. The user must be fully aware of the user instructions prior to use.
4. To be used with the parts and cables provided in accordance to the user instructions manual.
5. Do not block the vent of the device.
6. Not to be dissembled, repaired, or modified.
7. If device failure or abnormal behavior is suspected, stop using the device immediately and contact the head office.

#### 7.2.2 Installation Precautions

1. Not to be used with cables other than the ones provided with the device.
2. Do not turn on the device until installation is complete.
3. Do not block the cooling fan of the device.
4. Never use with ungrounded wall outlet.
5. To be installed on flat surfaces only.

#### 7.2.3 Precautions Before Device Use

1. Become fully aware of the device operation manual before use.
2. Inspect all parts before use.

#### 7.2.4 Precautions During Device In-Use

1. Never directly stare at the laser emitting part of the device.
2. Do not use this device in places where combustible steam or explosive gases and chemicals are present or stored.
3. If issues not listed in the user instruction manual have occurred, do not attempt to resolve them on your own; instead contact the head office.
4. Keep this device and other electronic devices away from liquids.
5. Do not bend, twist or shock the probe

6. Be careful not to touch the laser emitting part of the probe with bare hand as this will contaminate the lens.

### **7.2.5 Laser Safety**

1. Do not expose yourself to the laser of this device.
2. Never directly stare at the laser emitting end of the probe.

### **7.2.6 Maintenance Precautions**

1. Back up data on a regular basis to avoid data loss.
2. Update the software on a regular basis.
3. Leave the device turned off during moving, washing, or maintenance.

## **8. Study Evaluation**

### **8.1 Primary Endpoint**

The primary endpoints in this study are the agreement between cCeLL Ex vivo and frozen section, the sensitivity of cCeLL ex vivo and frozen section, and the specificity of cCeLL ex vivo and frozen section. These endpoints will be assessed by a single pathologist in the analysis of tumor tissue.

### **8.2 Secondary Endpoints**

1. Comparison of time taken in tissue scanning, visualization, and interpretation using cCeLL – Ex vivo to time taken in frozen section analysis.
2. Accuracy in determining the tumor type
3. Required image counts for adequate analysis and diagnosis using cCeLL – Ex vivo
4. Non-diagnostic Image
5. AUC value

### **8.3 Statistical Analysis and Interpretation**

#### **8.3.1 Methods and Sample Size**

The data for agreement, sensitivity and specificity can be summarized as in the table below. For agreement, the terms agree and disagree are with respect to each other. For sensitivity and specificity, the terms agree and disagree are with respect to truth. So for sensitivity, truth is tumor and for specificity truth is not tumor. It should also be noted that since the total sample size was chosen to be 250, no power calculations were done; however, a probability calculation that the estimated parameter is greater than the null hypothesis was presented.

**Agreement Table**

		cC		
FS Results	Agree	DisAgree		
	a	b	a+b	
Disagree	c	d	c+d	
		a+c	b+d	n T

The estimate of agreement is  $p_{AG} = (a+d)/n_T$ . It is desired to test the hypothesis that the agreement is greater than 80%. This is compatible with the expected result that both the sensitivity and the specificity will be about 90%. Thus the hypothesis to be tested is that the agreement is 80% (H0: Null hypothesis) versus the alternative hypothesis that the agreement is greater than 80% (HA: Alternative hypothesis).

$$H_0: \pi_{AG} = 80\% \text{ vs } H_A: \pi_{AG} > 80\%$$

Where  $\pi_{AG}$  is the percent agreement between Frozen Section and cCell. This will be tested utilizing the exact binomial test. Estimates of agreement from the pilot study indicate that the agreement will be greater than 86%. In this study, there will be 250 participants available for analysis for the estimation and testing of agreement. For outcome results, if the agreement is 86%, with the sample size of 250, the probability the estimated agreement will be greater than 80% is greater than 90%. That is,  $P(p_{AG} > 80\%) > 90\%$ .

**Sensitivity Table** – Sensitivity is only calculated when the truth standard is positive for tumor.

Agreement Table with Tumor Truth

		cC		
FS Results	Agree w/Truth	Disagree w/Truth		
	e	f	e+f	
Disagree	g	h	g+h	
		e+g	f+h	n T

The sensitivity of the Frozen Section is given by  $p_{SenF} = (e+f)/n_T$  and the sensitivity of cCell is given by  $p_{SenC} = (e+g)/n_T$ . It is desired to demonstrate that the sensitivity of cCell is non inferior to that of Frozen section.

The non inferiority of the sensitivity of cCell result versus the sensitivity of the Frozen Section is given as:

$$H_0: \pi_{SenF} - \pi_{SenC} > \Delta \text{ versus } H_A: \pi_{SenF} - \pi_{SenC} \leq \Delta$$

Here  $\pi_{SenF}$  is the true sensitivity for Frozen Section and  $\pi_{SenC}$  is the true sensitivity for cCell. The parameter  $\Delta$  is the non-inferiority limit. In this study, it is proposed to utilize a  $\Delta=0.05$  (5%). If that  $\Delta$  is used and the anticipated sensitivity for both Frozen Section and cCell is 90%, then

with a sample size of 200 tumor positive samples the probability the difference between the estimated sensitivities is less than 5% is greater than 90%. That is  $P((\pi_{\text{SenF}} - \pi_{\text{SenC}} \leq 5\%) > 90\%.$

**Specificity Table** – Specificity is only calculated when the truth standard is negative for tumor.

Agreement Table with Non-Tumor Truth

		cC		
FS Results	Agree w/Truth	Disagree w/Truth		
Agree	r	s	r+s	
Disagree	t	u	t+u	
		r+t	s+u	$n_2$

The specificity of the Frozen Section is given by  $p_{\text{SpeF}} = (r+d)/n_2$  and the specificity of cCeLL is given by  $p_{\text{SpeC}} = (r+d)/n_2$ . It is desired to demonstrate that the specificity of cCeLL is non-inferior to that of Frozen section.

The non-inferiority of the specificity of cCell result versus the specificity of the Frozen Section is given as:

$$H_0: \pi_{\text{SpeCF}} - \pi_{\text{SpeC}} > \Delta \text{ versus } H_A: \pi_{\text{SpeF}} - \pi_{\text{SpeC}} \leq \Delta$$

Here  $\pi_{\text{SpeF}}$  is the true specificity for Frozen Section and  $\pi_{\text{SpeC}}$  is the true specificity for cCell. The parameter  $\Delta$  is the non-inferiority limit. In this study, it is proposed to utilize a  $\Delta=0.10$  (10%). If that  $\Delta$  is used and the anticipated specificity for both Frozen Section and cCell is 90%, then with a sample size of 50 tumor negative samples the probability the difference between the estimated specificities is less than 10% is greater than 80%. That is  $P(\pi_{\text{SpeF}} - \pi_{\text{SpeC}} \leq 10\%) > 80\%.$

The sensitivity and the specificity hypotheses will be tested using McNemar's test by constructing an upper 97.5% confidence bound for the difference between the two methods. If the upper bound is less than  $\Delta$  (5% for sensitivity and 10% for specificity) then the two images are said to be non-inferior. The upper confidence bound is given by:

$$p_{\text{FS}} - p_{\text{cC}} + z_{0.05} \text{se}(p_{\text{FS}} - p_{\text{cC}}), \text{ where}$$

$$\text{se}(p_{\text{FS}} - p_{\text{cC}}) = \frac{\sqrt{(b+c)}}{n}$$

The standard error (se) for the difference depends on the number of discordant pairs (a and b). Where a and b correspond to f and g from the sensitivity table and to t and s from the specificity table. The estimates  $p_{\text{FS}}$  and  $p_{\text{cC}}$  correspond to the sensitivity of the Frozen Section,

$p_{\text{SenF}}$ , and the sensitivity of cCell,  $p_{\text{SenC}}$  when sensitivity is being tested and they correspond to the specificity of the Frozen Section,  $p_{\text{SenF}}$ , and the specificity of cCell,  $p_{\text{SenC}}$ , when specificity is being tested.

The secondary endpoints will be summarized via descriptive statistics. No hypothesis testing will be performed for the secondary endpoints.

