Sample Size	
The sample size refers to the number of analyzable tissue samples collected from participants. There may be multiple samples collected from each participant. As it is expected that the 30% of tissue samples will be non-analyzable, the collection of tissue samples will be larger than the target sample size.
 
The total samples to be collected will be up to 358 samples (286 cancer samples, 72 normal samples)
 

- Korea University Anam Hospital: 51 samples (cancer: 42 samples, normal: 9 samples)

	

- Seoul National University Hospital: 82 samples (cancer: 72 samples, normal: 10 samples)

- Samsung Medical Center: 82 samples (cancer: 72 samples, normal: 10 samples)

- St.Michael's Hospital, Unity Health: 143 samples collected from a total of 65 participants (cancer: 100 samples, normal: 43 samples)

 
After excluding the non-analyzable tissue samples, we expect to conclude the study with a total of 250 samples (200 samples for cancer, 50 samples for normal)
 

-Korea University Anam Hospital: 36 samples (cancer: 30 samples, normal: 6 samples)

-Seoul National University Hospital: 57 samples (cancer: 50 samples, normal: 7 samples)

-Samsung Medical Center: 57 samples (cancer: 50 samples, normal: 7 samples)

-St.Michael's Hospital, Unity Health: 100 samples collected from a total of 50 participants (cancer: 70 samples, normal: 30 samples)

																			

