Basis for Calculating the Number of Acquired Images	
The data for agreement, sensitivity and specificity can be summarized as in the table below. For agreement, the terms agree and disagree are with respect to each other. For sensitivity and specificity, the terms agree and disagree are with respect to truth. So for sensitivity, truth is tumor and for specificity truth is not tumor.
 
Agreement Table
 

	cC	

FS Results	Agree	DisAgree		

Agree	b	a+b	

Disagree	c	d	c+d	

	a+c	b+d	nT	

 
The estimate of agreement is <math>p_{AG} = (a+d)/n_T</math>. It is desired to test the hypothesis that the agreement is greater than 80%. This is compatible with the expected result that both the sensitivity and the specificity will be about 90%. Thus the hypothesis to be tested is:
 $H_0: \pi_{AG} = 80\% \text{ vs } H_A: \pi_{AG} > 80\%$ 
Where <math>\pi_{AG}</math> is the percent agreement between Frozen Section and cCeLL. This will be tested utilizing the exact binomial test. Estimates of agreement from the pilot study indicate that the agreement will be greater than 86%. In this study, there will be 250 subjects available for analysis for the estimation and testing of agreement. For outcome results, if the agreement is 86%, with the sample size of 250, the probability the estimated agreement will be greater than 80% is greater than 90%.
			cC		FS Results	Agree	DisAgree		Agree	b	a+b	Disagree	c	d	c+d		a+c	b+d	n T
		cC																		
FS Results	Agree	DisAgree																		
	Agree	b	a+b																	
Disagree	c	d	c+d																	
	a+c	b+d	n T																	

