### **5.4 Sample Size**

The sample size refers to the number of analyzable tissue samples collected from participants. There may be multiple samples collected from each participant.

There will be 250 analyzable tissue samples required (200 tumor positive and 50 normal) for this study.

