### **8.3.2 Analysis Population**

The analyses described above will be performed on the intent to analyze population. That is, all samples in that are collected and are analyzable by frozen section will be utilized in the analysis regardless of whether they were successfully analyzed by both methods.

A secondary analysis will be done on the primary endpoints on the samples that were analyzable by both methods.

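### The primary agreement test and the non-inferiority bounds treat 250 tissue samples as independent although a patient may give up to three; with positive within-patient correlation the type I error rises and may exceed its nominal level

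*Combined protocol and SAP*

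**What the plan says.** Section 8.3.1 tests a null agreement of 80% against a higher value: the parameter "is the percent agreement between Frozen Section and cCell. This will be tested utilizing the exact binomial test". For sensitivity and specificity it forms an upper bound for the paired difference, with standard error sqrt(b+c)/n computed from counts of discordant samples.

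The unit is the tissue sample. Section 5.4 requires 250 analyzable samples (200 tumor, 50 normal) and adds: "There may be multiple samples collected from each participant". Section 6.2 lists tumor center, normal tissue and margin, and says that "the number of sample tissues harvested will differ from minimum of one to maximum of three". Section 8.3.2 takes them all in: "all samples in that are collected and are analyzable by frozen section will be utilized in the analysis". For the Canadian site the Synopsis plans "100 samples collected from a total of 50 participants (cancer: 70 samples, normal: 30 samples"; section 5.4.1 gives 65 participants for the same 100 samples.

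The agreement text names a different unit. Section 8.3.1 says "In this study, there will be 250 participants available for analysis for the estimation and testing of agreement", and the Synopsis says "In this study, there will be 250 subjects available for analysis for the estimation and testing of agreement". Nothing in section 8.3 mentions within-patient correlation, a clustered variance, or a restriction to one sample per patient.

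**The concern.** Samples from one patient share the disease, the operation and the site pathology department, so frozen section and cCeLL may tend to agree, or disagree, on all of them together. In that case 250 samples carry less information than 250 independent observations. The exact binomial test and sqrt(b+c)/n would both understate the variance, and the chance of wrongly claiming agreement above 80%, or non-inferiority, would go up. This matters because the Synopsis says the study should show whether the technique could replace frozen section. Someone who read only the agreement text would take the 250 to be separate people and see no problem.

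**Working it through.** **Inputs from the documents.** Null agreement 80%, anticipated agreement 86%, n = 250 samples (section 8.3.1); one to three samples per patient (6.2); Canada 100 analyzable samples from 50 (Synopsis) or 65 (5.4.1) participants, 70 tumor and 30 normal; Korea 150 samples, 130 tumor and 20 normal (5.4.1).

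**Assumptions not in the documents.** One-sided alpha 2.5% for agreement (5% also shown); ICC 0.1 to 0.5; the number of samples per Korean patient; the split of Canadian samples among patients.

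**The plan's own figure.** With independent samples, P(estimate > 80% | true 86%) = P(X ≥ 201 | 250, 0.86) = 99.4%, consistent with the stated value of more than 90%. Under clustering it remains 97-99%.

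**The test if samples are independent.** At one-sided 2.5% it rejects at X ≥ 213: P(X ≥ 213 | 250, 0.80) = 2.12%, and power at 86% is 68.2%. At one-sided 5% it rejects at X ≥ 211, with error 4.53%. The exact test therefore has a little slack.

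**Is clustering certain?** In Canada, yes. For 100 samples from 50 people there are 100 − 50 = 50 extra samples, at most two per person, so at least 25 people give more than one. With 65 people there are 35 extra samples, so at least 18 do.

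**Type I error under clustering.** Design effect = 1 + ICC × (Σm²/Σm − 1), where m is the number of samples from a patient. The errors come from exact convolution of beta-binomial clusters at true agreement 80%, keeping the cut-off of 213.

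| Pattern | Σm²/Σm | Design effect, ICC 0.1 to 0.5 | Type I error, ICC 0.1 to 0.5 |
|---|---|---|---|
| Only 20 Canadian tumor pairs correlated | (210 + 80)/250 = 1.16 | 1.02 to 1.08 | 2.2-2.5% |
| Canada 65 people (35 pairs, 30 singles), Korea singles | (180 + 140)/250 = 1.28 | 1.03 to 1.14 | 2.3-2.9% |
| Canada 50 pairs, Korea singles | (150 + 200)/250 = 1.40 | 1.04 to 1.20 | 2.3-3.2% |
| Canada 25 triples and 25 singles, Korea singles | (175 + 225)/250 = 1.60 | 1.06 to 1.30 | 2.4-3.7% |
| Pairs at every site (125 patients) | 500/250 = 2.00 | 1.10 to 1.50 | 2.6-4.9% |
| One sample per tissue type: Canada 50 pairs, Korea 20 triples and 45 pairs (115 patients) | (380 + 180)/250 = 2.24 | 1.12 to 1.62 | 2.8-5.6% |

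With 50 Canadian pairs and Korean singles, the error passes 2.5% at an ICC of about 0.19. At one-sided 5% the same pattern gives 4.9-6.1% and passes 5% at an ICC of about 0.15.

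**Sensitivity bound.** Simulation with z = 1.96 (the 97.5% bound that the text describes), n = 200, true difference 5%, 400,000 runs, assumed discordance 10/14/18%:
- No clustering: 3.44/3.18/2.85%.
- 20 Canadian tumor pairs (70 tumor samples from 50 people), within-patient correlation 0.5: 4.14/3.88/3.48%. Clustering adds 0.70/0.70/0.63 points.
- The same data with a clustered standard error: 3.45/2.99/2.83%.

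So 0.94/0.68/0.35 points of the excess over 2.5% are there without any clustering.

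**Specificity bound.** The 30 Canadian normal samples can come from 30 different people among 50, so few repeats are expected.

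**The case against.** A reader might infer that any positive correlation makes the error rate too high. The documents do not support that. Because of the slack, 50 Canadian pairs at ICC 0.1 give 2.32% against 2.5%, or 4.85% against 5%, both below nominal. If only the 20 Canadian tumor pairs are correlated, 2.5% is not reached until an ICC of about 0.46.

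A reader might also infer an error more than twice nominal. If Canada gave 50 pairs and Korea 50 triples (100 patients), the error would be 3.0-6.6%. But 130 Korean tumor samples from 50 patients means that many of them give three tumor samples, hence several of one tissue type, which section 6.2 does not establish. That pattern is an outer limit only. The 4.9% and 5.6% in the table also need assumed Korean cluster sizes together with ICC 0.5.

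The ICC range itself has no basis in the documents, and agreement on normal tissue need not track agreement on the same patient's tumor. That is fair, and it is why the result is a range.

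On the sensitivity bound, a substantial part of the excess over 2.5% is unrelated to clustering: more than half at 10% discordance, about half at 14%, about a third at 18%. A clustered standard error will not bring that bound to 2.5%.

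Nor should the words participants and subjects be read as concealment. The Synopsis and sections 5.4 and 5.4.1 count samples openly; these are slips in terminology.

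What stands is the omission. The Canadian clustering is planned, the one-to-three rule applies at every site, Korea supplies 150 of the 250 samples with no patient count, and the plan cannot show that its primary test holds its level.

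**Conclusion.** The point holds in a conditional form and should be fixed before analysis. The primary test and the bounds assume independence that the design does not provide. With positive within-patient correlation the type I error rises above its independent value and may exceed nominal. On Canadian clustering alone the effect is small: 2.3-3.2% with 50 participants in pairs, 2.3-2.9% with 65, and up to 3.7% with an uneven split, against 2.1% if independent. It becomes material only if Korean patients also give several samples each: 2.6-4.9% with pairs everywhere, 2.8-5.6% with 115 patients. All of this rests on the assumed ICC of 0.1 to 0.5 and one-sided 2.5%. The sensitivity bound moves by about 0.6-0.7 points at correlation 0.5, and specificity probably little. The plan's probability statement for agreement is not affected. Confidence is high in the omission and much lower in the size of its effect.

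**What to change.** Keep the sample as the unit and make a patient-clustered analysis primary, with the participant number (section 6.3.1) as the cluster.

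- **Agreement:** use z = (p_AG − 0.80)/sqrt(0.80 × 0.20 × DE/n), where DE is the patient-clustered variance of p_AG divided by p_AG(1 − p_AG)/n, set to at least 1. In simulation (ICC 0 to 0.5) it ran at 1.95-2.55% for nominal 2.5%. An equivalent pre-specified method is fine if simulation shows that it holds its level; a plain clustered Wald test does not (3.1-4.4%). State the one-sided alpha.
- **Bounds:** replace sqrt(b+c)/n with the patient-clustered standard error of the paired difference.
- **Sensitivity analyses:** keep the exact binomial test and the unclustered bounds.
- **Reporting:** give the number of patients and of samples per patient for each endpoint.
- **Text:** in section 8.3.1 and the Synopsis, call the 250 units samples. Reconcile the Canadian counts. Section 5.4.1 has 143 collected samples from 50 people but 100 analyzable ones from 65, which cannot both be true; the Synopsis has the two counts the other way round.

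The cost is a few lines of text and code, since every specimen number already contains the participant number. If clustering exists, the chance of passing the agreement test falls. At true agreement 86% it is 68% if samples are independent, 60-67% with Canadian pairs only and 50-64% with pairs everywhere (ICC 0.5 to 0.1). That loss reflects the true precision of the data.
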